4.3 Pharmacokinetic Full Analysis Set

The Pharmacokinetic Full Analysis Set (PKFAS) will be comprised of all subjects in the FAS who underwent an abbreviated PK study.

5. STATISTICAL CONSIDERATIONS

Safety, efficacy, PK, HRQoL and immunogenicity data from the additional BAX326 naïve subjects (Cohort 2) will be analyzed together with the data from the previously treated subjects (Cohort 1).

The pediatric (< 12 years) and the adolescent/adult (≥ 12 years) data (i.e. age group 1) will be summarized separately and overall for all outcome measures except for analyses mentioned in section 10, section 11 and pharmacokinetic analyses (it turned out that only adults underwent an abbreviated PK study). Further analyses will occur between the age groups <6 years, ≥ 6 to <12 years, ≥ 12 to <18 and ≥ 18 (i.e. age group 2) for all outcome measures except for analyses mentioned in section 10, section 11.1 and pharmacokinetic analyses.

In case it is specified that analyses for a specific outcome measure will also be presented by treatment regimen, the summary statistics should be presented by individual treatment regimen (standard prophylaxis, modified prophylaxis, PK-tailored prophylaxis and on-demand treatment) as well as for overall prophylaxis (combined standard, modified and PK-tailored prophylaxis).

If a subject changes regimen during the course of the study, then the data from that subject will be analyzed under the initial allocated regimen until a change of regimen is recorded. Data recorded after this stage will be analyzed under the updated regimen.

In general, all efficacy, safety, PK, HRQoL and immunogenicity variables will be summarized using descriptive statistics. Continuous variables will be summarized by sample size [n], mean, standard deviation [SD], median, minimum, maximum, Q1 and Q3. Categorical variables will be summarized in frequency tables (n, frequencies, and percentages). Additional statistics which will be provided for specific endpoints will be described in the corresponding section.

5.1 Interim Analyses

An interim safety review may be performed after a minimum of 50 subjects have accumulated a total of at least 100 EDs to BAX326 for evaluation of long-term hemostatic efficacy, safety, immunogenicity and HrQoL.

5.2 Handling of Missing, Unused, and Spurious Data

Statistical techniques will not be used to identify and exclude any observations as outliers from the analyses. If data are considered spurious (e.g. for lack of biological plausibility), it will be documented along with the reason for exclusion and the analyses from which the data were excluded.

1. For subjects with multiple screening visits resulting in multiple values, the most recent screening visit will be used for analysis.
2. Subjects who withdraw prior to the last planned observation in the study period will be included in the analyses up to the time of withdrawal.
3. Extra measurements (such as unscheduled or repeat assessments) will not be included in the descriptive statistics, but will be included in subject listings.
4. If a subject's weight is missing from any infusion record, the subject's last recorded weight will be used to calculate the weight-adjusted dose.

Outcome specific handling of missing data are described in the relevant section. Unless otherwise specified, no action will be made to handle missing data (observed case).

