### 9.3 Withdrawal and Discontinuation

Any subject may voluntarily withdraw (ie, reduce the degree of participation in the study) consent for continued participation and data collection. The reason for withdrawal will be recorded on the Completion/Termination eCRF. Assessments to be performed at the termination visit (including in cases of withdrawal or discontinuation) are described in Section 10.6 and Section 21.2. The data collected on withdrawn subjects will be used in the analysis and included in the clinical study report.

Discontinuation (ie, complete withdrawal from study participation) may be due to dropout (ie, active discontinuation by subject) or loss to follow-up (ie, discontinuation by subject without notice or action). Additionally, the investigator and sponsor have the discretion to discontinue any subject from the study if, in their judgment, continued participation would pose an unacceptable risk for the subject, or if the subject does not meet the eligibility criteria but was inadvertently enrolled in the study.

Subjects will also be discontinued from further study participation for the following reasons:

- The subject has developed an inhibitor to FIX  $\geq$  0.6 BU confirmed at the central laboratory.

- The subject with chronic hepatitis B or C has developed ALT/AST levels exceeding 5 times the upper limit of normal which may be confirmed by repeating the test.
- The subject has developed clinical signs of a thrombotic event.
- The subject has experienced severe allergic reaction(s), e.g. anaphylaxis, upon exposure to BAX326.
- The subject has received an immunomodulating drug (eg,  $\alpha$ -interferon, corticosteroid agents at a dose equivalent to hydrocortisone greater than 10 mg/day) other than anti-retroviral chemotherapy during the course of the study.
- The subject requires major surgery which will be performed outside the scope of the surgery study (e.g site not participating in surgery study, surgery study completedxviii)
- The subject becomes pregnant (if the subject is female of childbearing potential, which is not likely in this study). IP exposure will be discontinued. Attempts will be made to follow her through completion of the pregnancy. The investigator will record a narrative description of the course of the pregnancy and its outcome.

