2.8 Study Stopping Rules

This study will be halted, pending further review by the sponsor, or stopped under the following circumstances:

- If two or more subjects develop a high titer inhibitory antibody > 5 BU confirmed by the central laboratory, or if two or more subjects develop anaphylaxis following exposure to BAX326 in studies BAX326 Pivotal 250901, BAX326 Pediatric 251101, and BAX326 Continuation 251001, the transition to BAX326 Continuation will be halted. Within 2 weeks of receipt of the second report, Baxalta may decide to halt the study.
- The study may be stopped following any of the planned interim safety reviews or at any time by the sponsor in case of unacceptable risks to subjects, in particular in case of inhibitor development, thrombotic events, or anaphylaxis.

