5.4 Definition of Visit Windows

All available values will be used in the statistical analysis independent of whether they are within or outside the pre-defined visit windows. No specific visit windows will be defined for the statistical analysis.

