8.2 Analysis of Secondary Safety Outcome Measures

A table will present the number (%) of subjects for the following safety endpoints: occurrence of inhibitory and (treatment emergent) total binding antibodies to FIX, occurrence of (treatment emergent) antibodies to CHO proteins and rFurin, occurrence of severe allergic reactions (e.g. anaphylaxis), and occurrence of thrombotic events.

As mentioned in section 12.7.1 of the protocol, indeterminate results of total binding antibodies to FIX, antibodies to CHO proteins or rFurin will be set to negative. Occurrence of treatment emergent total binding antibodies to FIX, antibodies to CHO proteins and rFurin is defined by more than 2-dilution increase as compared to levels at screening visit (e.g. negative to 1:80).

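### Read literally, SAP 5.2 item 3 keeps unscheduled and repeat tests out of the SAP 8.2 antibody table, which states no sample or confirmation rule, so a subject could be miscounted (minor)

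*SAP*

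**What the plan says.** - **SAP 5.2, item 3:** "Extra measurements (such as unscheduled or repeat assessments) will not be included in the descriptive statistics, but will be included in subject listings". No endpoint is exempted.
- **SAP 5:** "In general, all efficacy, safety, PK, HRQoL and immunogenicity variables will be summarized using descriptive statistics". Categorical variables go into frequency tables with counts and percentages.
- **SAP 8.2:** "A table will present the number (%) of subjects for the following safety endpoints". The list covers inhibitors, total binding antibodies to FIX, and antibodies to CHO proteins and rFurin. For all but inhibitors, indeterminate results become negative and treatment emergence is a rise of more than 2 dilutions from screening. No inhibitor titer is given. For no antibody does the section say which samples count or how a discordant retest is handled.
- **Protocol Table 12.7-1:** immunology testing every 3 months and at termination (with additional early visits for new subjects), plus event-driven tests in both cohorts.
- **Protocol 12.7.1.2:** an inhibitor of at least 0.6 BU is to be confirmed centrally within 2 weeks of site notification. A FIX-binding titer of at least 1:80 prompts an additional sample within 2 ± 1 weeks, and the subject continues.
- **Confirmation elsewhere:** the stopping rule (SAP 2.8) concerns subjects who "develop a high titer inhibitory antibody > 5 BU confirmed by the central laboratory". Discontinuation (Protocol 9.3) is for an inhibitor "confirmed at the central laboratory". SAE reporting (Protocol 12.1.1.1) sets the same condition.
- **SAP 5.4:** "All available values will be used in the statistical analysis independent of whether they are within or outside the pre-defined visit windows".

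**The concern.** The tests that item 3 sets aside are the ones on which the protocol relies to find or settle an antibody case. Routine visits are 3 months apart, so a test prompted by poor response to treatment, or a confirmatory sample due about 2 weeks after a positive, normally falls off schedule. If these results are dropped, the table for a secondary safety outcome rests on scheduled samples alone. It could then omit a positive that was found and include an inhibitor that did not confirm. Immunogenicity is in the study title and few cases are expected, so a single subject is visible in the result.

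**Working it through.** There is no stated figure to reproduce. The check sets the provisions side by side and then sizes one misclassified subject.

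**Step 1: does item 3 reach the antibody table?** SAP 5 names immunogenicity among the variables summarized descriptively and treats frequency tables as part of that. SAP 8.2 is such a table and exempts nothing. Protocol 14.3.2.3 asks for frequency counts and percentages and gives no sample or confirmation rule either. Read literally, yes.

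**Step 2: what follows for each kind of case?**

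| Case | Scheduled result | Unscheduled or repeat result | SAP 8.2 table, item 3 taken literally | Rest of the plan |
|---|---|---|---|---|
| (a) FIX-binding, anti-CHO or anti-rFurin | negative | positive, more than 2 dilutions above screening | not counted | meets the SAP 8.2 definition |
| (b) Inhibitor, at least 0.6 BU, not confirmed | positive | negative | counted | not an SAE and not a reason for discontinuation |
| Inhibitor, confirmed | positive | positive | counted | SAE and discontinuation |
| Inhibitor, found off schedule and confirmed | termination test normally follows | positive, then positive | counted if the termination test is positive | SAE and discontinuation |

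The last two rows show why a confirmed inhibitor is hard to lose: it is an SAE, and discontinuation normally brings termination immunology (Protocol 10.6, Table 12.7-1). A severe allergic reaction also leads to discontinuation (Protocol 9.3), so it normally brings that test too. Limb (a) therefore mainly concerns a FIX-binding positive found after, for example, an inadequately treated bleed (Protocol 11.3). For CHO and rFurin the only basis for off-schedule testing is the general event-driven row of Table 12.7-1.

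**Step 3: would removing item 3 alone be enough?** Not for (b). If all results are used in an ever-positive count and no confirmation rule is stated, the first positive still counts. Both a sample rule and a confirmation rule are needed.

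**Step 4: size of one subject.** Effect = 1/N.
- Planned N = 100 + 25 = 125 (SAP 2): 1/125 = 0.80 percentage points. Exact 95% intervals: 0/125 gives 0 to 2.91%; 1/125 gives 0.02 to 4.38%.
- N = 82 + 25 = 107: 1/107 = 0.93 points. The 82 are the subjects with Continuation data at the June 2013 cut-off (Protocol 6.5). This assumes that they are all of Cohort 1 and that exactly 25 new subjects enter.
- Age under 12 (a split that SAP 5 requires): 23 subjects were treated in the pediatric study (Protocol 6.5). With no new subject under 12, 1/23 = 4.35 points. With all 25 under 12, 1/(23 + 25) = 1/48 = 2.08 points. This assumes that all 23 transitioned and are analyzed as under 12. SAP 5 does not say which screening age defines the group.

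**The case against.** The strongest case is that item 3 was never meant for this table. Clinically indicated tests are rows of the protocol's own immunology schedule, and confirmatory samples are required by the protocol, so neither is obviously extra. SAP 8.2 counts subjects with an occurrence, whereas item 3 makes most sense as a guard against duplicate values in time-point summaries. SAP 5.4 says that all available values are used. The confirmation rule is in Protocol 12.7.1.2, and SAP 5.5 lists no departure from it.

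Much of this stands. For (a) the milder reading is open, and the SAP does not choose between the two. For (b) it is weaker, because item 3 names repeat assessments outright. SAP 5.4 concerns visit windows and says nothing about unscheduled or repeat tests. The rule in Protocol 12.7.1.1 that central results prevail settles disagreement between laboratories, not between a first test and its repeat.

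It also stands that Protocol 12.7.1.1 and 12.7.1.3 already require an in-laboratory confirmatory assay for FIX-binding, anti-CHO and anti-rFurin antibodies. That limits false positives among them, but does not restore a positive left out under (a).

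**Conclusion.** The point holds as a minor gap in specification. Under the literal reading, the antibody table can omit a non-inhibitor positive found only off schedule in a continuing subject who is negative at later scheduled visits. It can also count an inhibitor whose confirmatory repeat was negative and so disagree with the SAE table. One subject is worth 0.80 points at N = 125 and 2.1 to 4.3 points under age 12, on the stated assumptions.

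Three stronger readings are not supported:
- *That SAP 8.2 contradicts the protocol on confirmation.* It is silent, and Protocol 12.7.1.2 can be read into it.
- *That confirmed inhibitors would disappear from the report.* They are SAEs, lead to discontinuation and are normally retested at termination. All results also remain in the subject listings.
- *That a case was missed.* No document figure shows this. Protocol 6.5 reports two transient rFurin positives at 1:80 during this study, but not whether those samples were scheduled. They show only that the choice of samples can matter.

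**What to change.** Leave SAP 5.2 item 3 as it is for all other tables and add one sentence: *This rule does not apply to the occurrence endpoints in SAP 8.2.*

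In SAP 8.2 add: *All post-baseline central-laboratory antibody results (scheduled, clinically indicated and confirmatory) are used. An inhibitor is counted when it is at least 0.6 BU and confirmed as in Protocol 12.7.1.2; unconfirmed inhibitor positives are reported in a separate row and not counted. Treatment-emergent total binding, anti-CHO and anti-rFurin antibodies are counted by the existing more than 2-dilution definition applied to any post-baseline result. For FIX-binding antibodies, the counted cases are also broken down by whether the additional sample in Protocol 12.7.1.2 confirmed them.*

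Item 3 should not be narrowed to by-visit summaries. Laboratory shifts, vital signs, IR and HR QoL (SAP 8.2.1, 8.2.2, 9.1, 10.1) compare screening, baseline or pre-infusion with end of study, so that narrowing could let repeat values into those tables.

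The cost is a few SAP sentences. No new data are needed, because the results are already collected and listed.

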5.3 Definition of Baseline

The most recent value prior to first infusion of IP will be taken as baseline.

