#### 9.1.2 Newly Recruited Subjects (Cohort 2)

Newly recruited subjects who meet **ALL** of the following criteria are eligible for this study:

- Subject and/or legal representative has/have provided signed informed consent.
- Subject is 2 to 70 years old at the time of screening.
- Subject is naïve to BAX326
- Subject has severe (FIX level  $< 1\%$ ) or moderately severe (FIX level 1-2%) hemophilia B (based on the one stage activated partial thromboplastin time (aPTT) assay), as tested at screening at the central laboratory.
- Subject aged  $\geq 6$  years has been previously treated with plasma-derived and/or recombinant FIX concentrate(s) for a minimum of 150 EDs
- Subject aged  $< 6$  years has been previously treated with plasma-derived and/or recombinant FIX concentrate(s) for a minimum of 50 EDs.
- Subject has no evidence of a history of FIX inhibitors.

- Subject is immunocompetent as evidenced by a CD4 count  $\geq 200$  cells/mm^3 at screening.
- Subject is human immunodeficiency (HIV) negative or is HIV+ with a viral load  $< 200$  particles/ $\mu$ L  $\sim < 400,000$  copies/mL
- If female of childbearing potential, subject presents with a negative pregnancy test and agrees to employ adequate birth control measures for the duration of the study.
- Subject is willing and able to comply with the requirements of the protocol.

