### **11.1.3 Determination of Incremental Recovery Over Time in Newly Recruited Subjects and Subjects Receiving a PK-Tailored Dose**

FIX levels to determine IR will be assessed at the following visits:

- At ED1 (only newly recruited subjects)xxi
- At Week 4 ± 1
- At Month 3 ± 1 week
- Every three months ± 1 week
- At study termination/completion

---

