#### **14.3.2.2 Pharmacokinetics**

PK parameters will be calculated for all subjects planned to receive a PK-tailored treatment regimen using a non-linear mixed effects model approach.

The available PK data (FIX activity levels) from pivotal study 250901, pediatric study 251101 and surgery study 251002 will be utilized together in the model and strengthen the estimation of the full PK curve even if only sparse samples are available for an individual.

The following PK parameters for FIX will be reported using descriptive statistics: AUC0-∞ (area under the plasma concentration/time curve from time 0 to infinity), IR, T1/2 (elimination phase half-life), MRT (mean residence time), CL (clearance), Vss (Volume of distribution at steady state). Incremental recovery (IR) will be determined as the changes in FIX activity level from pre-infusion to 30 ± 5 minute post-infusion, divided by dose, and reported as (IU/dL)/(IU/kg). FIX activity levels at pre-infusion reported as < 1% will be used as 0.5% for the calculation of IR.

Incremental recovery of FIX will be summarized by visit and displayed graphically over time for each subject. Also the change from baseline (at screening visit) will be described using summary statistics. As the maximum dose can be 120 IU/kg any doses higher than 120 IU/kg are not allowed and therefore frequencies requiring a higher are excluded.

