**Table 21.1-1**  
**Flow Diagram of Required Procedures for Baxalta Clinical Study 251001**

- d) Post-infusion blood draw for FIX activity at 15-30 minutes for subjects transitioning from BAX326 Pediatric
- 11) Vital signs at  $30 \pm 5$  minutes and  $2 h \pm 10$  minutes following completion of the infusion

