**Table 21.1-1**  
**Flow Diagram of Required Procedures for Baxalta Clinical Study 251001**

**3. First Infusion in Newly Recruited Subjects (ED1)**

Once eligibility criteria are confirmed, the subject will receive the first infusion at the study site which will include an assessment of IR. For subjects planned to receive a PK-tailored dose regimen, please see procedures described for assessment of PK.

At least 5 days (120 hours), preferably 7 days, must have elapsed since the previous FIX administration and the subject must not be actively bleeding.

Procedures to be done **before the infusion**:

- 1) Review and discuss subject diary
- 2) Record AEs
- 3) Concomitant medication and non-drug therapy
- 4) Physical examination including weight
- 5) Assess HR QoL including Patient Activity Level and collect Health Resource Utilization items pre- or post-infusion of BAX326
- 6) Vital signs within 15 minutes of start of infusion

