5.5 Changes from the Planned Statistical Analysis in Protocol

The following changes from the planned statistical analysis in the protocol were made:

- In some instances, techniques will be used to adjust for missing data.
- In addition to the Full Analysis Set, a Per Protocol Analysis Set and a Pharmacokinetic Full Analysis Set were added.
- Pharmacokinetic parameters will be calculated using non-compartmental analysis (NCA), rather than a model combining data from this and previous studies, due to the lack of a suitable model.
- In order to determine the incremental recovery (IR) over time and see if antibodies have affected the recovery following long-term exposure, it is important to compare the end of study IR with the baseline IR. Therefore the IR will be summarized for baseline and end of study only rather than for all available time points.

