9.1 IR Over Time

Analysis of IR over time will be carried out on the FAS.

IR_{30min} in IU/dL/IU/kg will be calculated as:

$$\text{IR}_{30\text{min}} = \frac{C_{30\text{min}}[\text{IU/dL}] - C_{\text{pre-infusion}}[\text{IU/dL}]}{\text{dose per kg body weight [IU/kg]}}$$

where C_{30min} and C_{pre-infusion} relate to the unadjusted concentration values.

IR_{30min} of FIX will be summarized for baseline and end of study using descriptive statistics. Also the change from baseline to end of study will be described using summary statistics.

These tables will be created for the on-demand treatment only (i.e. subjects who received on-demand treatment exclusively over the whole study period), for the overall prophylaxis (combined standard, modified and PK-tailored prophylaxis) only, for subjects who received on-demand treatment and any prophylaxis treatment (i.e. subjects who switched during the study) as well as for all treatment regimens together.

In addition, IR_{30min} of FIX will be provided in a by-subject listing.

The maximum allowable dose is 120 IU/kg – all cases with a dosage higher than 120 IU/kg will be excluded from the IR tables and will be only displayed in a listing.

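### The baseline rules give no baseline incremental recovery (IR) for the naive Cohort 2, so these subjects drop out of the only IR change the SAP summarizes

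*SAP*

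**What the plan says.** **Baseline.** SAP 5.3 reads "The most recent value prior to first infusion of IP will be taken as baseline". It makes no exception by variable or cohort. For IR, protocol 14.3.2.2 says "Also the change from baseline (at screening visit) will be described using summary statistics".

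**Which IR summaries remain.** SAP 5.5 limits them: "Therefore the IR will be summarized for baseline and end of study only rather than for all available time points". The reason given there is to see whether antibodies have affected recovery after long exposure. SAP 9.1 then states "Also the change from baseline to end of study will be described using summary statistics". By-subject listings (SAP 9.1) and by-subject graphs (SAP 9.2) are also planned.

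**Cohort 2.** Protocol 9.1.2 requires "Subject is naïve to BAX326". In the IR schedule of protocol 11.1.3 the first entry is "At ED1 (only newly recruited subjects"). Item 3 of the flow diagram (Table 21.1-1) says of ED1 that "the subject will receive the first infusion at the study site which will include an assessment of IR".

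**Pediatric transfers.** Item 10d of the flow diagram has, for screening, "Post-infusion blood draw for FIX activity at 15-30 minutes for subjects transitioning from BAX326 Pediatric". Protocol 11.1.1 with Table 11.1-1, and footnote b of Table 21.3-1, give 30 ± 5 minutes for transitioning subjects with no pediatric exception.

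**The concern.** A recovery is the rise from a pre-infusion level to a level about 30 minutes after the infusion, divided by the dose. It cannot exist before the infusion that produces it. For a subject who has never had BAX326, no BAX326 recovery can precede the first infusion, so SAP 5.3 points to a value that is never collected.

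This matters because the SAP has dropped the intermediate visits and rests the summary of IR over time on one contrast. Cohort 2 is also the only cohort whose reference recovery can be measured at first exposure to BAX326; Cohort 1 was already exposed in the parent studies. Losing Cohort 2 from the change removes the subjects for whom the question in SAP 5.5 is cleanest. It also leaves the baseline and end-of-study columns describing different groups.

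The pediatric sampling time is a second, smaller issue. If baseline is drawn earlier after the infusion than end of study, recovery would appear to fall with no real change.

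**Working it through.** The plan gives no figure to reproduce here: SAP 2.6 has no sample-size calculation and IR is descriptive. The check has two parts.

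**A. Is there a baseline IR for Cohort 2?**

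1. Inputs to IR (SAP 9.1): pre-infusion level, 30-minute level, dose per kg. An infusion is required.
2. Screening of newly recruited subjects (flow diagram item 1b): FIX activity is drawn, but no infusion is listed. Table 21.4-1 has no FIX recovery at screening; the first is at ED1.
3. Table 21.2-2 does mark Incremental Recovery at screening. This conflicts with item 1b and Table 21.4-1. It could not be a BAX326 recovery in a naive subject before the first infusion.
4. SAP 5.3 therefore yields 0 baseline values in at least 25 subjects, and so does the protocol's screening-visit baseline.
5. SAP 11.2 names exposure day 1 as the reference for thrombin generation (TGA) in newly recruited subjects. SAP 9.1 has no equivalent for IR.
6. Share of the study: 25/(100 + 25) = 20%, or 25/100 = 25% if the total is about 100, as protocol 6.3 suggests.
7. Effect on the tables: SAP 5 pools the cohorts, protocol 8.6.3 gives Cohort 2 prophylaxis only, and SAP 5.2 uses observed cases. Cohort 2 thus enters the end-of-study rows for overall prophylaxis and for all regimens, but not the baseline or change rows. With the parent-study totals in protocol 6.5 as upper bounds (73 pivotal + 23 pediatric = 96), the all-regimens table could show up to 96 subjects at baseline and 96 + 25 = 121 at end of study.

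**B. How large could the pediatric timing effect be?**

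1. Windows after infusion: baseline 15-30 minutes (item 10d), end of study 25-35 minutes. The gap runs from 25 − 30 = −5 to 35 − 15 = +20 minutes. The midpoints differ by 30 − 22.5 = 7.5 minutes, and the windows overlap at 25-30.
2. One-compartment decline: overstatement of baseline IR = exp(ln 2 × gap / half-life) − 1. Half-lives are from the pivotal study (protocol 6.4.1; ages 12-59): median 24.58 h, range 15.83-52.34 h.

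| Half-life | 7.5 min | 15 min | 20 min |
|---|---|---|---|
| 15.83 h | 0.55% | 1.10% | 1.47% |
| 24.58 h | 0.35% | 0.71% | 0.94% |
| 52.34 h | 0.17% | 0.33% | 0.44% |

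3. On the anticipated IR of 0.7 under 12 years (protocol 6.1), 0.35% is 0.0025 and 1.47% is 0.0103 (IU/dL)/(IU/kg).
4. Sensitivity, on assumption only, since the documents give no distribution-phase parameters: with 20-60% of the initial level in a distribution phase of half-life 0.5-4 h and a terminal half-life of 24.58 h, the overstatement is 0.7-8.4% at 7.5 minutes and 1.4-18.3% at 15 minutes.
5. For scale, the pivotal-study IR was 0.87 with SD 0.22 (0.22/0.87 = 25%).
6. Pivotal transfers have 30 ± 5 minutes at both screening and end of study, so no gap arises. They are up to 73 of the 96 possible transfers (76%).

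**The case against.** On Cohort 2, the best defence is that SAP 5.3 is a general rule and any analyst would take the ED1 recovery. The data are collected, SAP 11.2 shows the intention for TGA, and nothing is lost that wording cannot restore. IR is also a descriptive measure without a test, and antibodies are measured directly every three months, so antibody detection does not depend on this contrast. All of that is fair and limits the consequence. It does not supply a rule: the revision history shows that sections 9.1 and 11.2 were revised together, yet only 11.2 names exposure day 1, and the protocol's own baseline fails in the same way.

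A reader might infer more: that the whole IR comparison is undefined or biased, or that children will show a false decline. The documents do not support either.

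- Cohort 1 has a baseline. Its screening recovery is transcribed from the parent-study termination visit and precedes the first infusion of this study proper. The pivotal transfers among them also have matching windows.
- For children, the 15-30 minute draw is one side of a contradiction. Two other places give 30 ± 5 minutes, the windows overlap, and the actual draw times come from a parent study whose protocol is not among these documents.
- A bias of several percent appears only under assumed distribution-phase parameters.

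**Conclusion.** The point holds for Cohort 2. Read literally, both baseline definitions leave at least 25 naive subjects, about 20-25% of the planned study, without a baseline IR. They are then absent from the only summarized IR change but present at end of study. This follows from the schedules alone, without numerical assumptions. It is a rule that misfires, not a loss of data.

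For pediatric transfers (at most 23, the parent-study total, not a count of those who transferred) the finding is an internal contradiction with a possible bias toward a false fall in IR. Its size is about 0.35-1.5% at the median and shortest reported half-lives, and less at the longest. That assumes one-compartment decline, half-lives from subjects aged 12 and over, and a baseline drawn earlier than end of study. It is small beside the between-subject spread.

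**What to change.** - In SAP 9.1, define baseline IR as the ED1 recovery for Cohort 2, as SAP 11.2 does for TGA, and as the screening (parent-study termination) recovery for Cohort 1.
- Summarize baseline, end of study and change on subjects with both values, so that the three describe the same group.
- Correct the Incremental Recovery mark at screening in Table 21.2-2.
- Reconcile flow diagram item 10d with Table 11.1-1 and Table 21.3-1 footnote b on the pediatric sampling time.
- Add a sensitivity summary of the pediatric IR change restricted to baseline draws at 25 minutes or later, using the actual sampling times SAP 9 already plans. As a sensitivity summary it does not breach the SAP 9 rule that timing deviations do not exclude observations. SAP 5 and SAP 9 should also agree on whether IR is split by age.

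Moving the pediatric baseline to Month 3 would also match the windows, but it could hide an early decline, so the restricted summary is preferable.

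The cost is a few sentences in the SAP, one derivation, one extra table and a protocol clarification. No new data are needed; the restricted pediatric summary will rest on fewer children.
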